2. SUBJECT POPULATION AND ELIGIBILITY

Subject Population – Inclusion criteria

- Previous participation in both Phase 1 and/or Phase 2 of the STRIDE (Sleep to Reduce Incident Depression Effectively, IRB 11586) clinical trial will serve as the recruitment entry point for this pilot study. Insomnia patients (DSM-5) will have all received standardized digital CBTI (dCBTI) (Sleepio) (Phase1). Although most insomnia patients respond to dCBTI, only ~50% fully remit. dCBTI non-remitters (ISI >7) and participants who were then re-randomized to standard face-to-face CBTI (Phase 2), but were still non-remittent, will be offered mindfulness-augmented CBTI (MBTI) delivered by nurse via telemedicine real-time video (Phase 3).
- Patients who were non-remittent following face-to-face CBTI with a Behavioral Sleep Clinician are also eligible to participate in the study. These would be identified using chart-review.
- No vulnerable populations will be involved, although participants who are Henry Ford employees will be offered the chance to participate if they meet the study criteria (still non-remittent for insomnia after dCBTI and/or face-to-face CBTI therapy).
- English literacy
- Participants must have access to a device (cell phone, computer, or tablet) with audio and video capability.

Enrollment and/or Screening

- Participants will be identified by:
 - 2-year follow-up questionnaires from STRIDE (Sleep to Prevent Incident Depression Effectively, IRB 11586). Participants must have an ISI (Insomnia

Severity Index) > 7 at the 2-year follow-up to qualify for this pilot study.

- Chart-review from HFHS Epic records
- Prospective participants will be approached by email and phone (Drake_MBTI-STRIDE_Recruiting Materials). No additional screening other than what has previously been described is necessary.

3. STUDY PROCEDURES

1. Potential participant is identified based on Insomnia Severity Index (ISI) score from STRIDE Timepoint 5 (2-year follow-up questionnaire), referral, or chart-review. ISI score greater than 7.
2. Prospective participant is contacted by email and/or phone and the additional study is described by the RN-Research Coordinator (RC) or Clinical Research Assistant (RA). Interested participants will be emailed the Informed Consent Form (ICF) in the form of a Qualtrics questionnaire. At the end of the Qualtrics questionnaire, the participant is given the option of a) Declining to participate, b) Agreeing to participate, or c) Expressing interest but would like more information. A video visit will be scheduled for the latter two options.
3. During the video visit, the RC or RA will review the ICF with the participant, explaining in detail the components of the study and answering all questions the participant has. If the participant would still like to move forward and participate, a second ICF Qualtrics questionnaire will be emailed with a signature page for the participant to sign and submit. A digital version of the HIPAA consent will also be discussed, and participants will be invited to sign. Participants will be able to have digitally signed copies of both documents for their records.
4. Once consent has been received, a baseline questionnaire (Drake_MBTI-STRIDE_Questionnaires) will be sent by email to the participant through the Qualtrics platform.
5. A tentative schedule for the 8 sessions will be determined and sent to the participant for reference. Schedules are flexible and can be changed by either the participant or the nurse therapist as required.
6. Eight sessions will be completed according to the Session Outlines (Drake_MBTI-STRIDE_Session Guide). Homework, consisting of a meditation log (Drake_MBTI-STRIDE_Participant Handouts) and a sleep diary (Drake_MBTI-STRIDE_MBTI Sleep Diary), are assigned to the participant each week for completion. Immediately prior to each session, a short Qualtrics questionnaire (Drake_MBTI-STRIDE_Treatment survey) will be emailed to the participant to complete; this questionnaire asks the participant questions about sleepiness, mood, and insomnia severity) to allow the clinician an opportunity to monitor the well-being of the participant each week.
7. At the conclusion of the eight sessions an end-of-study questionnaire (Drake_MBTI-STRIDE_Questionnaires) will be sent to the participant to complete.
8. Six months after completion of the treatment sessions, a 6-month follow-up questionnaire (Drake_MBTI-STRIDE_Questionnaires) will be sent to the participant to complete.

Additional Information

- Assessments will occur at baseline, at completion of the 8-week intervention, and 6 months following completion of the intervention.
- Data will be collected using questionnaires on the Qualtrics survey platform for the following assessments at Pre-Treatment, Acute Post Treatment and then 6-Month

Follow-up time points

- Insomnia Severity Index (ISI)
- PHQ9
- Five-Facet Mindfulness Questionnaire – a measure of mindfulness insight
- Pre-Sleep Arousal Scale (PSAS) – a measure of nocturnal cognitive arousal
- PSWQ – a measure of cognitive arousal
- RRS Brood – a measure of cognitive arousal
- Perseverative Thinking Questionnaire (PTQ) – a measure of repetitive negative thinking
- Epworth Sleepiness Scale (ESS)
- Daytime Insomnia Symptom Response scale (DISRS)
- COVID-19 Questions
- Data analysis plan:
 - Power Analysis: Although MBTI produces large reductions in insomnia symptoms in prior trials (Cohen's $d > .80$), patients in this study are treatment resistant. Therefore, we anticipate that MBTI may have a reduced effect on insomnia symptoms. Based on a medium anticipated effect (Cohen's $d = .50$) for a two-tailed test with alpha = .05, a N = 34 sample size will have a .81 power to detect significant effects using within samples t-tests. To account for potential subject attrition, we thus request to recruit a sample size of 40 participants. Notably, in many of our prior insomnia therapy trials, attrition rates were <5%, therefore we are confident that a N=40 sample size will provide sufficient power to detect symptom changes in our primary and secondary outcomes
 - AIM 1: We will use an intent-to-treat approach using the last observation carried forward, which is a conservative method to address missing data/attritors in clinical trials. We will test changes in insomnia symptoms using paired-samples t-tests from pre to post MBTI. We will use a two-tailed test with significance set at alpha=0.05. Cohen's d will be used to describe effect size.
 - AIM 2: Analyses for Aim 2 will be the same as those for Aim 1, except we will examine changes in cognitive arousal.
 - The team member performing the statistical analysis will be provided with de-identified demographic data and questionnaire answers.
- Therapy Content
 - Session-by-session outlines –Drake_MBTI-STRIDE_Session Guide
 - Participant handouts – Drake_MBTI-STRIDE_Participant Handouts
- Treatment Fidelity:
 - For this project, [name] will be supervised by the PI, [name], who is a licensed clinical psychologist with extensive training and clinical practice in CBT, mindfulness-based interventions, and MBTI. In addition, MBTI sessions will be audio-recorded as permitted by the participant. After study completion, 5% of these sessions will be randomly selected ($40*6*.05=10$ sessions) and rated for fidelity by [name].
- Nurse Therapist: [name], PhD, is the therapist delivering the intervention to subjects. In addition to providing Cognitive Behavioral Therapy for Insomnia as the research therapist since February, 2014, she has completed the following training in Mindfulness:

- Mindfulness-Based Stress Reduction (8-week course through the Beaumont Center for Mindfulness)
- Mindfulness-Based Cognitive Therapy (8-week course through Brown University School of Public Health)
- 5-Day MBSR Silent Retreat through the Beaumont Center for Mindfulness
- MBSR Foundations to become a Mindfulness-Based Stress Reduction teacher (8-week masters-level course through Brown University School of Public Health) which prepares individuals to begin teaching workshops in mindfulness-based interventions
- Additional certificate level training includes:
 - MBSR: Mindfulness-Based Stress Reduction (PESI, a 2-day program)
 - Integrating mindfulness-based stress reductions (MBSR) skills in clinical practice: A retreat (PESI)
- She has received direct training in Mindfulness-Based Therapy for Insomnia (MBTI) from Drs. [name] and [name].

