**Mindfulness-Augmented Cognitive Behavioral Therapy for
Insomnia as a Phase 3 Treatment for Non-remittent Insomniacs
- An Open-label Pilot Study**

NCT03724305

March 8th 2023

1. Statistical Analysis Plan

Study outcomes were downloaded directly from Qualtrics and all analyses were performed in SPSS 241 version 26 (IBM Corp) with a significance value of .05. We first examined descriptive data for sample 242 characteristics, including sociodemographics, insomnia treatment history, and presenting clinical symptoms. 243 Study hypotheses were tested using a complete case analysis approach, which included all patients enrolled in 244 MBTI. As the study was a single-arm proof-of-concept clinical trial, we conducted paired samples t-tests to test 245 acute pretreatment to posttreatment effects of MBTI on mindfulness, sleep symptoms, depression, and cognitive 246 arousal. To test long-term effects, we conducted paired samples t-tests comparing study outcomes at 247 pretreatment and 6-month follow-up. Paired samples t-test effect sizes are expressed using Cohen's dz; 248 small=.20, medium=.50, large=.80, very large ≥ 1.00 . In addition, we conducted posthoc analyses to further 249 explore our data, which included examining frequency of Rx and OTC sleep aid use at posttreatment and 250 follow-up (note: reducing sleep aid use can be a goal of insomnia therapy, but this was not the case in the 251 present study; rather we observed spontaneous changes in sleep aid use), as well as rates of insomnia remission 252 and major depression among patients with high vs low cognitive arousal at posttreatment and follow-up.

2. Protocol

1. **STUDY AIM, BACKGROUND, AND DESIGN ABSTRACT**

Millions of people with untreated insomnia suffer from impaired daytime functioning, depression, and poor quality of life. Cognitive-behavioral therapy for insomnia (CBT-I) is a specialist-driven multicomponent treatment that is recommended as a first-line intervention with superior safety and durability relative to pharmacotherapy. Despite the demonstrated success of CBT-I, ~50% of patients do not achieve full remission.

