4. ANTICIPATED RISKS

Risks include (1) excessive sleepiness and (2) rare mild emotional distress related to participants experiencing potentially distressing thoughts and emotions. Mood and sleepiness are both monitored through weekly questionnaires, the therapy process, and sleep diaries. Additional precautions include bi-weekly consultation with clinical psychologists who are part of the research team and one who is not directly involved in the study ([name]). Participants who show significant psychological distress will be removed from the study and referred to Behavioral Health. Low risk-Medium benefit.

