10. WITHDRAWAL OF SUBJECTS

- Participants may choose to withdraw from the study at any time.
- The PI may determine that the participant should be terminated from the study if he believes the study is not in the participant's best interest.
- Participants may be asked to meet, virtually or in person, with study staff for safety reasons.
- If a participant withdraws or is terminated from the study, data gathered up until that point may be kept for analysis.

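### Participants removed for distress or terminated by the PI leave with no planned later outcomes; if they do worse, the complete-case test overstates improvement, slightly at the expected attrition

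*Combined protocol and SAP*

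**What the plan says.** **Timing of outcomes.** Protocol section 3, item 7, places the post-treatment questionnaire as follows: "At the conclusion of the eight sessions an end-of-study questionnaire". Item 8 places the last one: "Six months after completion of the treatment sessions, a 6-month follow-up questionnaire". The summary under Additional Information gives baseline and then "at completion of the 8-week intervention, and 6 months following completion of the intervention". None of these says what happens to someone who stops sessions but stays in the study.

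**Exit.** Section 4 states: "Participants who show significant psychological distress will be removed from the study and referred to Behavioral Health". The same section describes the anticipated risk as "rare mild emotional distress related to participants experiencing potentially distressing thoughts and emotions". Section 10 adds a second route: "The PI may determine that the participant should be terminated from the study". For anyone who withdraws or is terminated, it says that "data gathered up until that point may be kept for analysis". It describes no collection after that.

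**Analysis.** The SAP states: "Study hypotheses were tested using a complete case analysis approach, which included all patients enrolled in" MBTI. The protocol's data analysis plan (section 3) instead names intent-to-treat with last observation carried forward (LOCF). It justifies 40 recruits by a need for 34, and cites attrition below 5% in many of the team's earlier trials.

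**The concern.** Removal for distress is not a random loss. The SAP tests depression and cognitive arousal alongside sleep symptoms, and psychological distress overlaps with the first two. A participant who deteriorates on a tested outcome can therefore be taken out before the post-treatment score is collected, and a complete-case paired t-test then leaves that person out. The mean change among those who remain looks better than the mean change among those enrolled. With one arm, no control group can show or offset this.

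At stake is the size of the pre-post effect and, to a lesser degree, the error rate of its test. Safety information is not at stake, because adverse-event reporting still captures distress. The point also does not depend on the SAP and the protocol naming different missing-data methods. The gap is in what is collected.

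**Working it through.** **Inputs from the documents.** 40 recruited, 34 needed, so an allowance of 6; expected attrition below 5%, so fewer than 2 of 40, that is at most 1; planned effect d = 0.50; two-tailed alpha 0.05; paired t-test.

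**Assumed inputs.** The documents give nothing on how leavers fare. I use a gap of 0.5 or 1.0 SD between completers' and leavers' mean change or, alternatively, a correlation rho of 0.2, 0.3 or 0.5 between the tendency to leave and poor change. All effects are in SDs of change.

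**The plan's own figure.** Power with N = 34 and d = 0.50: noncentrality 0.50 × √34 = 2.915, 33 df, critical t 2.035. Power is 0.808, which reproduces the stated 0.81.

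**Bias for a given gap.** With k leavers, the all-enrolled mean is (1 − k/40) × completer mean + (k/40) × leaver mean. Hence

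overstatement = (k/40) × (completer mean − leaver mean).

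**Null error rate.** Call it false improvement: a significant result in the direction of benefit when the mean change over all 40 is zero, nominally 2.5%. The completer mean is then (k/40) × gap. The rate is the probability that a noncentral t with 39 − k df and noncentrality (k/40) × gap × √(40 − k) exceeds its 0.975 critical value.

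| Leavers | Gap (SD) | Overstatement (SD) | Noncentrality | False improvement |
|---|---|---|---|---|
| 0 | any | 0 | 0 | 2.5% |
| 1 | 0.5 | 1/40 × 0.5 = 0.0125 | 0.078 | 3.0% |
| 1 | 1.0 | 1/40 × 1.0 = 0.025 | 0.156 | 3.5% |
| 6 | 0.5 | 6/40 × 0.5 = 0.075 | 0.437 | 6.2% |
| 6 | 1.0 | 6/40 × 1.0 = 0.150 | 0.875 | 13.3% |

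**Bias for a given correlation.** If the k people highest on a latent tendency to leave do leave, the overstatement is rho × k × E/(40 − k), where E is the mean of the top k of 40 standard normals: 2.16 for k = 1 and 1.51 for k = 6.

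- One leaver, rho 0.2 / 0.3 / 0.5: 0.011 / 0.017 / 0.028 SD; false improvement 2.9 / 3.3 / 3.8% (100,000 simulated trials per setting).
- Six leavers: 0.053 / 0.080 / 0.133 SD; false improvement 5.0 / 6.9 / 12.9%.

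**Would LOCF repair it?** The survey before each session covers sleepiness, mood and insomnia severity. It does not list the cognitive-arousal scales, so for Aim 2 the value carried is baseline and the leaver's change is set to zero. The estimate is then 34/40 of the complete-case one. With six leavers and a true effect of 0.50:

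| rho | Complete case | LOCF, baseline carried | False improvement, LOCF |
|---|---|---|---|
| 0.2 | 0.50 + 0.053 = 0.55 | 0.85 × 0.553 = 0.47 | 5.0% |
| 0.3 | 0.50 + 0.080 = 0.58 | 0.85 × 0.580 = 0.49 | 6.9% |
| 0.5 | 0.50 + 0.133 = 0.63 | 0.85 × 0.633 = 0.54 | 12.8% |

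Under these assumptions LOCF gives an estimate closer to 0.50, but its null error rate is practically that of complete case. Zeros leave the sum and the sum of squares of the changes unaltered, so the t statistic hardly moves. For Aim 1 a pre-session insomnia score could be carried. If it holds half of the leaver's own change (assumed), the estimates are 0.48 / 0.50 / 0.52 and the rates 3.5 / 4.1 / 5.8%.

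**The case against.** The strongest reply is that nothing may have been lost. The SAP says that its complete-case set took in all patients enrolled. Read literally, nobody was missing and the bias is zero. The wording is also compatible with incomplete cases having been dropped, and the documents report no attrition, so it settles the matter neither way.

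Second, the effect at the plan's own expectation is negligible: at most about 0.028 SD, or 0.028/0.50 = about 6% of the planned effect. Six leavers is the recruitment cushion, not a forecast, and the protocol describes distress as rare and mild. This stands, and it sets the priority. The overlap of distress with outcome is also clearest for depression and cognitive arousal. The documents do not tie distress to a worse insomnia change, which is the Aim 1 outcome.

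Third, LOCF would do better than complete case on the estimate. That is true under the assumed correlations. But the SAP does not use LOCF, and with baseline carried it leaves the null error rate where it was.

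A reader might also infer that both questionnaires are restricted to people who complete all eight sessions. The text does not support that. Items 7 and 8 fix when the questionnaires go out, not who may receive them, and the protocol plans an intent-to-treat analysis. For people who stop sessions but stay in the study, the plan is silent.

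**Conclusion.** The concern holds for participants removed for distress or terminated by the PI. As written, the plan provides for no outcomes after their exit, and the SAP then tests complete cases. If they do worse than completers, improvement is overstated by about 0.03 SD or less with one leaver and by 0.075 to 0.15 SD with six leavers and a gap of 0.5 to 1.0 SD. If nobody was lost, the overstatement is zero. The gaps and correlations are assumptions; only the 40, the 34, the expected attrition and the test come from the documents.

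It would go too far to infer that the trial's result is materially biased. That needs losses near the six-person allowance as well as clearly worse leavers, and the documents show neither. This is a minor point with a cheap improvement.

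**What to change.** 1. In section 4, change removal from the study to removal from treatment with referral to Behavioral Health, and let questionnaire follow-up continue unless the participant declines. Apply the same to PI termination in section 10, unless contact itself is judged harmful.
2. State that everyone enrolled is sent both questionnaires. Leave items 7 and 8 as they are for completers. For others, send the post-treatment questionnaire on the date planned for session 8 (or on stopping, if later) and the last one six months after that. Where no schedule was set, 8 weeks after baseline is a reasonable date (my suggestion).
3. Include these replies in the primary analysis.
4. Report the number of exits with reasons, and the number who did not reply. For scores still missing, add a sensitivity analysis with change set 0.5 and 1.0 SD below completers (my values).

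**Cost.** A short amendment, a sentence in the consent form, and two existing online questionnaires per leaver: 2 with one leaver, 12 with six. Each contains the PHQ-9, so some replies may trigger the depression and suicidality process in section 12, more likely among people removed for distress. Some leavers will not reply, perhaps selectively, and the effect estimate may be smaller. Who is taken off treatment and referred does not change.

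The SAP is written in the past tense. If collection has ended, items 1 and 2 come too late, but item 4 can still be done.

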4. ANTICIPATED RISKS

Risks include (1) excessive sleepiness and (2) rare mild emotional distress related to participants experiencing potentially distressing thoughts and emotions. Mood and sleepiness are both monitored through weekly questionnaires, the therapy process, and sleep diaries. Additional precautions include bi-weekly consultation with clinical psychologists who are part of the research team and one who is not directly involved in the study ([name]). Participants who show significant psychological distress will be removed from the study and referred to Behavioral Health. Low risk-Medium benefit.

5. ANTICIPATED BENEFITS

Anticipated benefits include a new treatment option for people who have been shown to be resistant to sleep improvement from standard CBTI and an improvement in cognitive-emotional distress that may be contributing to poor sleep. In turn, this may lower the risk of depression and other disorders related to poor sleep.

An additional treatment option would be beneficial in that it offers hope to those who have not had success with other methods.

6. RENUMERATION/COMPENSATION

No monetary compensation will be provided.

7. COSTS

We do not anticipate there being any costs for participation.

8. ALTERNATIVES

Alternatives for taking part in this study include participants talking their doctor, getting treatment in a clinical setting, participating in another research study, or getting no treatment.

9. CONSENT PROCESS AND DOCUMENTATION

- a. The consent will be presented in a Qualtrics questionnaire format. At the end of the Qualtrics questionnaire, the participant is given the option of a) Declining to participate, b)

Agreeing to participate, or c) Expressing interest but would like more information. A video visit will be scheduled for the latter two options.

- b. During the video visit, the Research Coordinator (RC) or Research Assistant (RA) will review the ICF with the participant, explaining in detail the components of the study, the participant's responsibilities, and answering all questions the participant has. If the participant would still like to move forward and participate, the participant will be invited to sign the Qualtrics questionnaire. A completed ICF will be emailed to the participant for their record.
- c. Prospective participants will have all the time they need to answer the questions so long as recruitment is still occurring.
- d. A digital copy of the consent will be stored in a password-protected folder on the HFHS shared drive.

10. WITHDRAWAL OF SUBJECTS

- Participants may choose to withdraw from the study at any time.
- The PI may determine that the participant should be terminated from the study if he believes the study is not in the participant's best interest.
- Participants may be asked to meet, virtually or in person, with study staff for safety reasons.
- If a participant withdraws or is terminated from the study, data gathered up until that point may be kept for analysis.

